7.4 INTERIM ANALYSES

In order to ensure the patient's safety during the trial, an external DMC, independent of the trial and project teams, will be set-up to review all available un-blinded safety data as well as selected efficacy data at regular intervals following first-patient-in. A separate DMC SAP

Proprietary confidential information © 2022 Boehringer Ingelheim International GmbH or one or more of its affiliated companies

will be produced which describes the analyses required for assessment by the DMC. Further details will be provided in a DMC charter.

As the primary aim of this study is to collect long-term safety and efficacy data on the use of BI 655130 (SPESOLIMAB) in this population, multiple interim analyses will be done over the 7-year conduct phase of this trial to support, for example, regulatory interactions, CTA and MAA/BLA submissions, but also to provide important safety and efficacy information to the sponsor to guide further development of the compound, and to the investigators via IB updates and publications.

A CTR describing all data collected within this trial will be produced once the last patient in the trial has completed the final follow-up visit.

7.5 HANDLING OF MISSING DATA

Every effort will be made to collect complete data at all visits. However, missing data will still occur and approaches to handle this are proposed below.

For the safety data, including the primary endpoint, no missing data imputations are planned.

For efficacy data, if one or more subscores on the clinical remission (or clinical response), calculated using the Mayo Clinic score, are missing at a visit then the overall outcome at that visit is also considered to be missing.

With regards to the handling of missing data on those efficacy outcomes derived from the MCS, no missing data imputations are planned to be performed.

If a patient experiences disease worsening during the re-induction period, or a disease flare during the maintenance period prior to observing the efficacy outcome at a specific visit, then all data subsequent to the intake of such rescue medication will be set to missing. Additional summaries including all data observed even following rescue medication intake will also be done. Further details with regard to what constitutes a rescue intake with potential impact on the efficacy data will be described in the TSAP.

For other efficacy endpoints, rules for handling of missing data will be specified in the TSAP if necessary.

7.6 RANDOMISATION

Given the single arm nature of this trial, no randomization will be performed.

7.7 DETERMINATION OF SAMPLE SIZE

Given the descriptive nature of this trial, no sample size calculation has been performed.

Approximately 160 patients who meet the entry criteria are planned for inclusion into this trial, rolling over from the preceding trials of 1368-0005 part 1 and 1368-0004.

8. INFORMED CONSENT, TRIAL RECORDS, DATA PROTECTION, PUBLICATION POLICY, AND ADMINISTRATIVE STRUCTURE

The trial will be carried out in compliance with the protocol, the ethical principles laid down in the Declaration of Helsinki, in accordance with the ICH Harmonized Tripartite Guideline for Good Clinical Practice (GCP), relevant BI Standard Operating Procedures (SOPs), the EU regulation 536/2014 the Japanese GCP regulations (Ministry of Health and Welfare Ordinance No. 28, March 27, 1997) and other relevant regulations.

Standard medical care (prophylactic, diagnostic and therapeutic procedures) remains the responsibility of the treating physician of the patient.

The investigator will inform the sponsor immediately of any urgent safety measures taken to protect the trial patients against any immediate hazard, as well as of any serious breaches of the protocol or of ICH GCP.

The Boehringer Ingelheim transparency and publication policy can be found on the following web page: trials.boehringer-ingelheim.com. The rights of the investigator and of the sponsor with regard to publication of the results of this trial are described in the investigator contract. As a rule, no trial results should be published prior to finalization of the Clinical Trial Report.

The certificate of insurance cover is made available to the investigator and the patients, and is stored in the ISF.

8.1 TRIAL APPROVAL, PATIENT INFORMATION, INFORMED CONSENT

This trial will be initiated only after all required legal documentation has been reviewed and approved by the respective Institutional Review Board (IRB) / Independent Ethics Committee (IEC) and competent authority (CA) according to national and international regulations. The same applies for the implementation of changes introduced by amendments.

Prior to patient participation in the trial, written informed consent must be obtained from each patient (or the patient's legally accepted representative) according to ICH / GCP and to the regulatory and legal requirements of the participating country. Each signature must be personally dated by each signatory and the informed consent and any additional patient-information form retained by the investigator as part of the trial records. A signed copy of the informed consent and any additional patient information must be given to each patient or the patient's legally accepted representative.”

The investigator must give a full explanation to trial patients based on the patient information form. A language understandable to the patient should be chosen, technical terms and expressions avoided, if possible.

The patient must be given sufficient time to consider participation in the trial. The investigator obtains written consent of the patient's own free will with the informed consent form after confirming that the patient understands the contents. The investigator must sign (or

Proprietary confidential information © 2022 Boehringer Ingelheim International GmbH or one or more of its affiliated companies

place a seal on) and date the informed consent form. If a trial collaborator has given a supplementary explanation, the trial collaborator also signs (or places a seal on) and dates the informed consent.

Re-consenting may become necessary when new relevant information becomes available and should be conducted according to the sponsor's instructions.

The consent and re-consenting process should be properly documented in the source documentation.

8.2 DATA QUALITY ASSURANCE

A quality assurance audit/inspection of this trial may be conducted by the sponsor, sponsor's designees, or by IRB / IEC or by regulatory authorities. The quality assurance auditor will have access to all medical records, the investigator's trial-related files and correspondence, and the informed consent documentation of this clinical trial.

8.3 RECORDS

CRFs for individual patients will be provided by the sponsor. For drug accountability, refer to [section 4.1.8](#).

8.3.1 Source documents

In accordance with regulatory requirements the investigator should prepare and maintain adequate and accurate source documents and trial records that include all observations and other data pertinent to the investigation on each trial patient. Source data as well as reported data should follow good documentation practices and be attributable, legible, contemporaneous, original and accurate. Changes to the data should be traceable (audit trail). Data reported on the CRF must be consistent with the source data or the discrepancies must be explained.

The current medical history of the patient may not be sufficient to confirm eligibility for the trial and the investigator may need to request previous medical histories and evidence of any diagnostic tests. In this case the investigator must make three documented attempts to retrieve previous medical records. If this fails a verbal history from the patient, documented in their medical records, would be acceptable.

During the site visit the sponsor's CRA or auditor must be granted access to the original patient file (please see [section 8.3.2](#)). The investigator must ensure that all patient identifiers (e.g. patient's name, initials, address, phone number, social security number) have properly been removed or redacted from any copy of the patients' source documents before sending them to the sponsor.

If the patient is not compliant with the protocol, any corrective action e.g. re-training must be documented in the patient file.

For the CRF, data must be derived from source documents, for example:

Proprietary confidential information © 2022 Boehringer Ingelheim International GmbH or one or more of its affiliated companies

- Patient identification: gender, year of birth (in accordance with local laws and regulations)
- Patient participation in the trial (substance, trial number, patient number, date patient was informed)
- Dates of patient's visits, including dispensing of trial medication
- Medical history (including trial indication and concomitant diseases, if applicable)
- Medication history (if applicable)
- Adverse events and outcome events (onset date (mandatory), and end date (if available))
- Serious adverse events (onset date (mandatory), and end date (if available))
- Concomitant therapy (start date, changes)
- Originals or copies of laboratory results and other imaging or testing results, with proper documented medical evaluation (in validated electronic format, if available)
- Completion of patient's participation in the trial" (end date; in case of premature discontinuation document the reason for it).
- Prior to allocation of a patient to a treatment into a clinical trial, there must be documented evidence in the source data (e.g. medical records) that the trial participant meets all inclusion criteria and does not meet any exclusion criteria. The absence of records (either medical records, verbal documented feedback of the patient or testing conducted specific for a protocol) to support inclusion/exclusion criteria does not make the patient eligible for the clinical trial.

8.3.2 Direct access to source data and documents

The sponsor will monitor the conduct of the trial by regular on-site monitoring visits and in-house data quality review. The frequency of site monitoring will be determined by assessing all characteristics of the trial, including its nature, objective, methodology and the degree of any deviations of the intervention from normal clinical practice.

The investigator /institution will allow site trial-related monitoring, audits, IRB / IEC review and regulatory inspections. Direct access must be provided to the CRF and all source documents/data, including progress notes, copies of laboratory and medical test results, which must be available at all times for review by the CRA, auditor and regulatory inspector (e.g. FDA). They may review all CRFs and informed consents. The accuracy of the data will be verified by direct comparison with the source documents described in [section 8.3.1](#). The sponsor will also monitor compliance with the protocol and GCP.

8.3.3 Storage period of records

Trial site(s):

The trial site(s) must retain the source and essential documents (including ISF) according to contract or the local requirements valid at the time of the end of the trial (whatever is longer).

Sponsor:

The sponsor must retain the essential documents according to the sponsor's SOPs.

8.4 EXPEDITED REPORTING OF ADVERSE EVENTS

BI is responsible to fulfil their legal and regulatory reporting obligation in accordance with regulatory requirements.

8.5 STATEMENT OF CONFIDENTIALITY AND PATIENT PRIVACY

Individual patient data obtained as a result of this trial is considered confidential and disclosure to third parties is prohibited with the exceptions noted below. Patient privacy will be ensured by using patient identification code numbers.

Data protection and data security measures are implemented for the collection, storage and processing of patient data in accordance with the principles 6 and 12 of the WHO GCP handbook.

Treatment data may be given to the patient's personal physician or to other appropriate medical personnel responsible for the patient's welfare. Data generated as a result of the trial need to be available for inspection on request by the participating physicians, the sponsor's representatives, by the IRB / IEC and the regulatory authorities.

8.5.1 Collection, storage and future use of biological samples and corresponding data

Measures are in place to comply with the applicable rules for the collection and future use of biological samples and clinical data, in particular

- The BI-internal facilities storing biological samples from clinical trial participants as well as the external banking facility are qualified for the storage of biological samples collected in clinical trials.
- An appropriate sample and data management system, incl. audit trail for clinical data and samples to identify and destroy such samples according to ICF is in place
- A fit for the purpose documentation (biomarker proposal, analysis plan and report) ensures compliant usage
- A fit for purpose approach will be used for assay/equipment validation depending on the intended use of the biomarker data

8.6 TRIAL MILESTONES

The **start of the trial** is defined as the date when the first patient in the whole trial signs informed consent.

The **end of the trial** is defined as the date of the last visit of the last patient in the whole trial (“Last Patient Out”). The “**Last Patient Drug Discontinuation**” (LPDD) date is defined as the date on which the last patient at an individual trial site ends trial medication (as scheduled per protocol or prematurely). Individual investigators will be notified of SUSARs occurring with the trial medication until 30 days after LPDD at their site. **Early termination of the trial** is defined as the premature termination of the trial due to any reason before the end of the trial as specified in this protocol.

Temporary halt of the trial is defined as any unplanned interruption of the trial by the sponsor with the intention to resume it.

Suspension of the trial is defined as an interruption of the trial based on a Health Authority request.

The IEC / competent authority in each participating EU member state will be notified about the trial milestones according to the respective laws.

A final report of the clinical trial data will be written only after all patients have completed the trial in all countries (EU or non-EU) to incorporate and consider all data in the report.

The sponsor will submit to the EU database a summary of the final trial results within one year from the end of a clinical trial as a whole, regardless of the country of the last patient (EU or non-EU).

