The maintenance dose strength of 300mg s.c. was selected based on the assumed need for lower BI 655130 (SPESOLIMAB) exposures once a response or remission has been induced, as shown for other biologics in the IBD area. It is supported by the favourable bioavailability of the s.c. relative to the i.v. formulation (approx. 70%; cf. [section 6.2 of \[c03320877\]](#)). The dosing interval of q12w was initially selected based on the phase I findings of a long half-life (4-5 weeks) and sustained target engagement ($\geq 90\%$ as compared to baseline for at least 22 weeks after the last dose administered; [\[c03320877\]](#)). However, regular medical review meetings by the sponsor during the study conduct have demonstrated loss-of-response rates in initial responders after dose reduction to maintenance dosing, which were higher than those found with approved regimens. Under the assumption of a positive dose response relationship and given the favourable safety profile of BI 655130 (SPESOLIMAB) even at several fold higher IV doses (up to 1200mg q4w for up to 24 weeks), the sponsor has amended the trial to increase the *regular* maintenance dose to 300mg SC every 4 weeks, and the *intensified* maintenance dose after flare treatment to 600mg q6w.

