5.2.6.2 Adverse event collection and reporting

AE Collection

The investigator shall maintain and keep detailed records of all AEs in the patient files. The following must be collected and documented on the appropriate CRF(s) by the investigator:

- From the time of first dose of trial drug administration in the extension trial until the individual patient's end of trial:
all AEs (serious and non-serious) and all AESIs.
- After the individual patient's end of trial:
the investigator does not need to actively monitor the patient for new AEs but should only report any occurrence of cancer and trial treatment related SAEs and trial treatment related AESIs of which the investigator may become aware of by any means of communication, e.g. phone call. Those AEs should be reported on the BI SAE form (see [Figure 5.2.6.2:1](#)), but not on the CRF.

[figure not shown]

Figure 5.2.6.2: 1 Adverse event collection and reporting

However, patients who discontinue trial medication prematurely and agree to be contacted further should be followed up as described in [section 3.3.4.1](#), withdrawal from trial treatment. From then on until the initially planned completion date of each individual patient the investigator must report all deaths/fatal AEs regardless of relationship, related SAEs and related AESIs the investigator becomes aware of.

AE reporting to sponsor and timelines

The investigator must report SAEs, AESIs, and non-serious AEs which are relevant for the reported SAE or AESI, on the BI SAE form immediately (within 24 hours) to the sponsor's unique entry point (country specific reporting process will be provided in the ISF). The same timeline applies if follow-up information becomes available. In specific occasions the investigator could inform the sponsor upfront via telephone. This does not replace the requirement to complete and send the BI SAE form.

With receipt of any further information to these events, a follow-up SAE form has to be provided. For follow-up information the same rules and timeline apply as for initial information.

Information required

For each AE, the investigator should provide the information requested on the appropriate eCRF pages and the BI SAE form, if applicable.

The following should also be recorded as an (S)AE in the CRF and BI SAE form (if applicable):

- Worsening of the underlying disease or of other pre-existing conditions

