6. INVESTIGATIONAL PLAN

6.1 VISIT SCHEDULE

All patients are to adhere to the visit schedule as specified in the [Flow Charts](#). Each visit date (with its window) up to EOT is to be counted from Day 1. If any of these visits has to be rescheduled, the date of subsequent visit should be calculated from Day 1. EOT refers to the last dose administration of BI 655130 (SPESOLIMAB) at week 336. Additional visits for the purpose of re-testing of laboratory parameters or AE monitoring may be included as deemed necessary by the investigator.

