6.2.3 Follow up period and trial completion

For all patients, termination of trial medication and trial completion must be recorded on the corresponding eCRF.

For patients completing the safety FU period, the EOS visit is scheduled at 16 weeks after the last dose of study drug. For more details please follow [Flow Charts](#).

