7.3.4 Safety analyses

Adverse events will be coded using the Medical Dictionary for Drug Regulatory Activities (MedDRA). Standard BI summary tables and listings will be produced. All adverse events with an onset between start of treatment and end of the residual effect period (REP), a period of 16 days after the last dose of trial medication, will be assigned to the on-treatment period for evaluation. Adverse events occurring in the maintenance and re-induction periods will be separately described.

All treated patients will be included in the safety analysis. In general, safety analyses will be descriptive in nature and will be based on BI standards. No hypothesis testing is planned.

Statistical analysis and reporting of adverse events will concentrate on treatment-emergent adverse events, i.e. all adverse events occurring between start of treatment and end of the residual effect period. For patients who switch directly to maintenance treatment at week 12 of the re-induction period, adverse events occurring on and after the first day of maintenance treatment will be included in summaries of the maintenance period only. Adverse events that start before first drug intake and deteriorate under treatment will also be considered as 'treatment-emergent'. For all subjects who received disease flare treatment with BI 655130 (SPESOLIMAB), safety assessments including adverse events, laboratories, vital signs etc. which occurred subsequent to such intake will be excluded from presentations according to the planned treatment; these data will, however, be included in summaries where all data after any use of BI 655130 (SPESOLIMAB) are displayed.

Frequency, severity, and causal relationship of adverse events will be tabulated by system organ class and preferred term after coding according to the current version of the Medical Dictionary for Drug Regulatory Activities (MedDRA) at the database lock.

Laboratory data will be analysed both quantitatively as well as qualitatively. The latter will be done via comparison of laboratory data to their reference ranges. Values outside the reference range as well as values defined as clinically relevant will be summarised.

Laboratory data will be analysed descriptively with regard to distribution parameters as well as with regard to frequency and percentage of patients with abnormal values or clinically relevant abnormal values

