### **Overall Maintenance Treatment Period**

The overall maintenance treatment period applies to all patients taking at least one dose of maintenance treatment regardless of flare occurrence. This period will be considered to understand long-term efficacy and safety of spesolimab.

Table 6.1: 4 Flow chart of analysis phases for overall maintenance treatment period

Study analysis phase	Description	Start (included)	End (included)
Screening  phase	Screening	Earliest of (Date of informed consent, first screening procedure)	Date/time of injection of first maintenance study drug minus 1 minute
Maintenance treatment phase & Residual effects period	Maintenance on-treatment period	Date/time of injection of first maintenance study drug (Day 1 for maintenance)	Date of end of (infusion or injection) of last administered spesolimab + 112 days at 23:59
Follow-up  phase	Off-treatment period	Date of end of (infusion or injection) of last administered spesolimab + 113 days at 12:00 a.m.	Latest of: i) Date of End-of-Study visit; ii) last contact date on End of Study page at 23:59

Dates are defined individually per patient. If more than one date is associated with a specific visit, measurements associated with a specific date are assigned to a study analysis phase according to the rules specified in the table. An analysis phase will not extend beyond the start date of the following phase.

 The off-treatment period (i.e. Follow-up phase) only exists if the trial completion date is after the date of end of last injection or infusion + 112 days.

 The screening phase does not exist for re-induction treated patients who subsequently receive maintenance treatment.

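### Protocol 8.6 stops SUSAR notification 30 days after a site's last patient ends trial medication, while that patient's safety follow-up can run about 82 days longer

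*Protocol*

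**What the plan says.** Protocol 8.6 (Trial milestones) fixes the end of SUSAR communication to sites: "Individual investigators will be notified of SUSARs occurring with the trial medication until 30 days after LPDD at their site". It defines LPDD at site level, as "the date on which the last patient at an individual trial site ends trial medication (as scheduled per protocol or prematurely").

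The site's duties run longer. Protocol 6.2.3 states that "the EOS visit is scheduled at 16 weeks after the last dose of study drug". Protocol 5.2.6.2 requires all adverse events and AESIs to be collected over this period: "From the time of first dose of trial drug administration in the extension trial until the individual patient's end of trial". It also requires SAEs and AESIs to reach the sponsor within 24 hours. For a patient who completes treatment, Protocol 6.1 makes EOT and the last dose the same day: "EOT refers to the last dose administration of BI 655130 (SPESOLIMAB) at week 336".

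The two documents differ on how long after the last dose a patient counts as on treatment. SAP 6.1, Table 6.1:4 (overall maintenance treatment period) ends the on-treatment period at "Date of end of (infusion or injection) of last administered spesolimab + 112 days at 23:59". Protocol 7.3.4 describes the residual effect period as "a period of 16 days after the last dose of trial medication".

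**The concern.** The investigator's obligations and the sponsor's flow of SUSARs to that investigator end at different times, and no reason is given. After day 30 the investigator still has to recognise events, judge causality and report serious ones promptly.

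Protocol 5.2.6.1 tells investigators to weigh, among other things, the drug's known pharmacology and what is already attributed to its class. A new SUSAR from another site or trial bears directly on that judgement. Causality also decides some of what is reported. Under Protocol 5.2.6.2, once a patient's trial has ended, only cancers and treatment-related SAEs and AESIs need be reported.

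Because LPDD is a site-level date, the 30 days can start at one site while other sites are still dosing. Re-induction non-responders are withdrawn from treatment (Protocol 3.3.4.1). In Protocol Table 1.4:5, 1 + 2 + 4 + 2 = 9 of 10 + 16 + 14 + 10 = 50 re-induced patients had a clinical response at week 12. A site whose patients have all stopped would leave the notification list while SUSARs could still arise elsewhere. The documents do not show how many sites are in that position.

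**Working it through.** The documents give no figure for this gap, so there is none to reproduce.

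**Inputs**
- End of notification: LPDD + 30 days (Protocol 8.6).
- Follow-up: 16 weeks after the last dose (Protocol 6.2.3), 16 × 7 = 112 days.
- Scheduled days: EOT 2353 and EOS 2466 with a +7-day window (Protocol Flow Chart 1B; SAP Table 6.7:2), 2466 − 2353 = 113 days, or up to 120.
- g: days between a patient's last dose and LPDD at the site (not in the documents, so varied).

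**Formula**

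Uncovered days = max(0, T − 30 − g), where T is follow-up in days after the last dose. Uncovered share = uncovered days / T.

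**Last dose on LPDD (g = 0)**
- T = 112: 82/112 = 73.2%.
- T = 113 (scheduled days): 83/113 = 73.5%.
- T = 120 (end of the EOS window): 90/120 = 75.0%.

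**Patient stopped before LPDD (T = 112)**
- g = 28: 54/112 = 48.2%.
- g = 56: 26/112 = 23.2%.
- g ≥ 82: 0%.

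**LPDD dated later than the last dose**

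If ending trial medication is dated one dosing interval after the last dose (an assumption), the same formula applies to the last patient as well:
- 28 days: 54/112 = 48.2%.
- 42 days: (112 − 30 − 42)/112 = 40/112 = 35.7%.

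**Which on-treatment window?**

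Against the SAP's 112 days, the gap for g = 0 lies wholly inside the on-treatment period. Against the 16 days in Protocol 7.3.4, no on-treatment day is uncovered, since 30 > 16. The mismatch itself does not depend on this label, because the protocol's own follow-up and adverse event collection run to 16 weeks either way.

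**The case against.** **Other channels remain.** A reader might infer that sites receive no new safety information after day 30. The documents do not say that. Protocol 8.6 limits only SUSAR notification. Protocol 7.4 describes information to investigators through Investigator's Brochure updates and publications, Protocol 5.2.3 provides real-time laboratory results, the DMC reviews safety data, and Protocol 8.4 states a general expedited-reporting duty. None carries a 30-day limit. This objection stands against the broad reading. It does not remove the point, because laboratory results concern the site's own patients, the DMC advises the sponsor, and 8.4 does not promise site notification after day 30.

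**73% is not typical.** A reader might take it as the share for follow-up in general. It is a ceiling for the last patient or patients at each site. Patients stop at different times, and many may be fully covered. This stands.

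**Pharmacology.** It is tempting to argue that the drug is still fully active at day 30. Protocol 4.1.2 gives a half-life of 4-5 weeks and target engagement of at least 90% "as compared to baseline for at least 22 weeks after the last dose administered". Under single-exponential decline, 2^(−30/28) = 48% to 2^(−30/35) = 55% would remain at day 30. These are phase I findings, with the half-life from healthy volunteers. The Global Amendment 4 rationale allows for higher clearance in ulcerative colitis and a half-life of about 4 weeks or shorter. The point therefore does not rest on these figures. If 22 weeks set the need, notification to EOS would also fall short.

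**Neuropathy.** Protocol Table 1.4:1 reports three cases from ongoing spesolimab trials. It does not call them unexpected or say that they arose outside this trial, and any suspected case is already an AESI. They cannot be used to show that the 30-day limit caused or would cause a missed event.

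**Consequence.** By LPDD no patient at the site is being dosed, so no dosing decision there is affected. The primary endpoint counts treatment-emergent events whatever their judged cause, so its calculation does not depend on SUSAR letters. This stands and sets the priority.

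**Conclusion.** The point holds in a limited form. SUSAR notification to a site ends 30 days after LPDD, follow-up and reporting duties for its last patient continue to 112 days after the last dose, and nothing explains the difference. The gap is up to 82 of 112 days (73.2%) if the last dose falls on LPDD. It would be 36% to 48% if LPDD is dated one dosing interval later, and it shrinks to nothing for patients who stopped at least 82 days before LPDD. Using the scheduled EOS day and its window instead of exactly 112 days raises the ceiling slightly, to between 73.5% and 75.0%.

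The documents do not support reading this as a loss of all safety information, as a general 73% gap, or as a threat to any endpoint, estimate or dosing decision. It is a low-priority matter of follow-up vigilance, worth correcting because long-term safety is the first objective and the correction is cheap. The conflict between the 16-day and 112-day residual effect periods is a separate inconsistency.

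**What to change.** In Protocol 8.6, replace the 30-day limit so that investigators are notified of SUSARs until the last patient at their site has completed the EOS visit. The uncovered share then falls to 0%. Where the last dose falls on LPDD, notification runs 82 days longer than now on a 112-day follow-up, or 112 − 30 = 82 to 120 − 30 = 90 days allowing for the EOS window. If the sponsor prefers to keep 30 days, 8.6 should give the reason.

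The cost is one changed sentence and a longer distribution period in the existing SUSAR process. No patient visit or procedure is added.

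Separately, reconcile the 16-day residual effect period in Protocol 7.3.4 with the 112 days in SAP 6.1, so that both documents use the same on-treatment definition.
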